7.11. ADDITIONAL ANALYSES

7.11.1. Subgroup Analysis

An analysis of the primary endpoint and select secondary endpoints will be conducted by country to determine if there is a different treatment effect in the United Kingdom as compared to the United States. For this analysis, separate models will be constructed per subgroup.

Other primary endpoint and select secondary endpoint subgroups to be evaluated include: Sponsor name utilized in ICF (Sponsor name in ICF vs Sponsor not in ICF), Prohibited Concomitant Medication Use (Used vs Not Used), the subset of confounding protocol deviations as noted in section 7.10.3 of the RCT SAP (see Appendix 1), specifically, a change in medication that mimics symptoms of Parkinson's disease occurred, a change in medication used to treat motor and/or non-motor symptoms of Parkinson's disease occurred and/or data was collected at a visit performed out of window when the participant was not treating when protocol requires (Present, Not Present).

[figure not shown]
7.12. ADDITIONAL SUPPORTING ANALYSES

7.12.1.1. Supportive analysis to further explore clinical significance

Although the structure and methodology for data collection of the MDS-NMS allows for interpretation of the statistically significant changes to be interpreted as inherently clinically meaningful, the scale is relatively new and not well known. As such, to support future clinical adoption by referring physicians, a supplementary analysis is planned as part of the procedures specified in the Statistical Analysis Plan for SNS-PD-002 to establish the MCID for the MDS-NMS. The MCID value identified in the analysis for SNS-PD-002 will define the MCID for analysis in these supporting analyses.

To support the clinical significance of the primary endpoint, the responder rate (i.e., percentage that demonstrate change scores during the first treatment period of the OLE \geq the MCID) in the passive-active treatment group will be reported. Additionally, a McNemar's test will be employed to determine if the responder rate is statistically significantly greater after 12 weeks of tvCVS treatment during the OLE than was the responder rate for this group after 12 weeks of passive treatment during the RCT. The required percentage of participants during the OLE tvCVS that demonstrate a change exceeding the MCID to be statistically significant will be a function of the percentage of participants in the passive-active treatment group that demonstrate a change exceeding the MCID after passive treatment during the RCT. This relationship is depicted in Figure 2. Because the power of this binomial comparison will be reduced under conditions where there is a high responder rate of passive treatment participants during the RCT, if 36% or more of the RCT passive treatment group exceeds the MCID (a condition that would require > 60% responder rate in the active group), the clinical significance for the primary outcome measure will be established by verifying that the

mean difference between responses to the passive treatment RCT and the tvCVS treatment in the OLE exceeds the change equivalent to the MCID.

Effect of Percent in Placebo Group Exceeding MCID

Figure 1: Effect of Percent in Passive (i.e., aka placebo or inactive) Group Exceeding MCID.

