Once the MCID is determined, it can be used to calculate the percentage of cases that exceed that value for each of the two treatment arms (i.e., responder rates). To further support clinical adoption, a supporting Fisher's exact test analysis will be employed to determine if the responder rate for active treatment participants is statistically significantly greater than the response rate for passive treatment participants. For statistical significance, the required percentage of participants in the intervention group that demonstrate a change exceeding the MCID will be a function of the percentage of participants in the passive treatment group that demonstrate a change exceeding the MCID. This relationship is depicted in Figure 3. Because the power of this binomial comparison will be reduced under conditions where there is a high rate of passive treatment participants that exceed the MCID, if 36% or more of the passive treatment arm exceeds the MCID (a condition that would require > 60% responder rate in the active arm), clinical significance for the primary outcome measure will instead be further supported by verifying that the mean/median difference between the two treatment arms exceeds the change equivalent to the MCID.

[figure not shown]

Figure 3: Effect of Percent in Passive Group Exceeding MCID on the Required Percent of Active Group Needing to Exceed MCID to demonstrate statistical significance using binomial comparison.

Additional analyses of the primary endpoint measure to support clinical adoption will include the following:

• The percent change of scores (normalized to the average baseline)

The percent change of scores is calculated as the mean change score divided by the mean baseline value multiplied by 100.

• The percentage of participants who improved by 1 MCID or more (i.e., change from baseline in MDS-NMS Total Score at Day 113 ≥ MCID calculated on an individual level). Participants who do not meet this criterion are non-responders.

The proportion of participants whose change from baseline to Day 113 in NMS-MDS total score met or exceeded the MCID will be summarized by treatment group.

• Effect Sizes

Effect size will be calculated in two ways:

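### The OLE responder analysis applies a two-arm 36% / 60% rule to a paired McNemar test, where the passive rate alone does not fix the rate required

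*SAP*

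**What the plan says.** **OLE SAP 7.12.1.1.** The responder rate in the passive-active group is to be reported, and "a McNemar's test will be employed to determine if the responder rate is statistically significantly greater after 12 weeks of tvCVS treatment" than after passive treatment in the RCT. The OLE rate required for significance "will be a function of the percentage of participants in the passive-active treatment group" who exceed the MCID on passive treatment. The switch follows: "if 36% or more of the RCT passive treatment group exceeds the MCID", glossed as "a condition that would require > 60% responder rate in the active group", then "the clinical significance for the primary outcome measure will be established by verifying" that the mean difference between the two treatment periods exceeds the MCID. No discordance, within-person correlation or sidedness is given for the McNemar test.

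**RCT SAP 7.7.1.3.** For the two randomised arms, "a supporting Fisher's exact test analysis will be employed". The same 36% trigger appears, with the gloss "a condition that would require > 60% responder rate in the active arm". The consequence is worded more softly: "clinical significance for the primary outcome measure will instead be further supported by verifying" the mean or median difference.

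**Related text.** OLE SAP 7.8.2.2 treats a statistically significant primary result as sufficient for clinical meaningfulness. OLE SAP 7.8.2.2.1 already plans the comparison with the MCID as a supportive analysis, without any condition. OLE SAP section 4 expects 74 participants in the passive-active group. OLE SAP 7.1 makes tests two-sided at 0.05 unless stated otherwise.

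**The concern.** Fisher's test compares two independent proportions, so for a given sample size the passive count fixes the active count needed. McNemar compares the same people with themselves. Only those whose responder status changes between periods carry information, and the same two marginal rates can be clearly significant or not significant depending on how many people changed in each direction. A rule indexed only by the passive rate cannot describe that test. The OLE SAP nevertheless uses one to decide which result is said to carry clinical significance.

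What is at stake is the responder claim that this section is meant to supply for clinical adoption. The two branches ask different questions (a paired difference in proportions, or a mean difference larger than an MCID) and can disagree on the same data. The trigger is also stated for the RCT passive group, while McNemar can use only those with data from both periods.

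**Working it through.** **1. Where the 60% figure comes from.** Inputs from RCT SAP section 4: 83 per arm, two-sided alpha 0.05, planned power of about 90%. Passive rate 36%. Pooled normal approximation for two independent proportions:

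power = Φ{ [(p2 − p1) − 1.96·√(2·p̄(1−p̄)/n)] / √([p1(1−p1) + p2(1−p2)]/n) }

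- p2 = 0.609, p̄ = 0.4845: (0.249 − 1.96 × 0.0776) / 0.0751 = 1.29, power 90%.
- p2 = 0.600, p̄ = 0.480: (0.240 − 1.96 × 0.0776) / 0.0753 = 1.17, power 88%.

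So a figure above 60% reproduces as a two-sample power threshold (60.9% at 90% power). The SAP does not state the power behind it. Read literally as the observed rate that reaches significance, it does not reproduce even for two arms: against 30/83 passive responders, Fisher's test is significant at 42/83 (50.6%, one-sided) or 44/83 (53.0%, two-sided).

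**2. Observed boundary for the test the OLE actually plans.** 74 pairs and 27 passive responders (27/74 = 36.5%, the smallest count at or above 36%, since 26/74 = 35.1%). Let c be the number who responded only on passive and b the number who responded only on active treatment. The exact one-sided p is P(X ≥ b) for X ~ Bin(b + c, 0.5), doubled for two-sided. The OLE rate is (27 − c + b)/74. For each c, take the smallest b with p < 0.05:

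| Passive-only responders c | Smallest b, two-sided | OLE rate, two-sided | Smallest b, one-sided | OLE rate, one-sided |
|---|---|---|---|---|
| 0 | 6 | 33/74 = 44.6% | 5 | 32/74 = 43.2% |
| 5 | 15 | 37/74 = 50.0% | 13 | 35/74 = 47.3% |
| 12 | 25 | 40/74 = 54.1% | 23 | 38/74 = 51.4% |
| 17 | 32 | 42/74 = 56.8% | 30 | 40/74 = 54.1% |
| 25 | 42 | 44/74 = 59.5% | 40 | 42/74 = 56.8% |
| 26 | 44 | 45/74 = 60.8% | 41 | 42/74 = 56.8% |
| 27 | 45 | 45/74 = 60.8% | 42 | 42/74 = 56.8% |

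At one passive rate, the two-sided boundary spans 16.2 percentage points. It passes 60% only when 26 or 27 of the 27 passive responders stop responding. One-sided, it never does.

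**3. Power reading for the paired test.** The documents give no correlation of responder status between periods, so phi is assumed from 0.5 to −0.4. With p1 = 0.36, P(both) = p1·p2 + φ·√[p1(1−p1)p2(1−p2)]; passive-only is p1 − P(both) and active-only is p2 − P(both). At p2 = 0.60 the root is √(0.2304 × 0.24) = 0.235. Exact McNemar power, 74 pairs, two-sided:

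| Phi | Passive-only / active-only at 36% vs 60% | Power at 36% vs 60% | OLE rate for 80% power | OLE rate for 90% power |
|---|---|---|---|---|
| 0.5 | 0.026 / 0.266 | 98.6% | 53.5% | 56.0% |
| 0 | 0.144 / 0.384 | 79.1% | 60.5% | 64.0% |
| −0.4 | 0.238 / 0.478 | 65.1% | 64.5% | 68.5% |

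Negative values cannot be dismissed. Under OLE SAP 7.4 the RCT end-of-treatment score (day 113) is the OLE baseline. It therefore closes the passive change and opens the active change, so its measurement error enters the two with opposite sign.

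**The case against.** - **A reader might infer that McNemar is dropped at 36%.** The text does not say so. The responder rate and the McNemar test are planned without condition, and the word instead appears in the RCT version only. What changes is the result by which clinical significance is said to be established. Since 7.8.2.2.1 already plans the mean-versus-MCID comparison, much of the remedy is already in the SAP.
- **A reader might infer a choice made on data already seen.** The RCT is to be analysed while the OLE runs, so the passive rate can be known early. But trigger and consequence are both written in advance and the trigger does not use the OLE result, which leaves no discretion. Nor is the fallback shown to be easier: if the true mean difference equals the MCID, its point estimate exceeds the MCID only about half the time.
- **A reader might infer that 60% is simply too high, or that the RCT rule is wrong.** Neither is established. The SAP gives power as its reason, and on that reading the RCT figure reproduces. For the paired test under independence, 60% gives 79.1% power two-sided and 87.5% one-sided, so it is not absurd. With negative correlation it is too low.
- **The figure behind the rule was not available for this review.** Its inputs could not be checked, so a carry-over from the RCT is an inference from matching numbers and near-matching sentences.

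All of this limits the point. None of it supplies a basis for a rule indexed only by the passive rate in a paired test.

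**Conclusion.** The concern holds for the threshold and the wording. The same pair of numbers serves a two-arm Fisher test and a within-person McNemar test, and for the latter the statement that the passive rate determines the rate required is incorrect. At 27 of 74 passive responders, the rate needed for significance is 44.6% to 60.8% two-sided or 43.2% to 56.8% one-sided; for 90% power, two-sided, it is 56.0% to 68.5%. These results assume 74 complete pairs, the exact conditional McNemar test at 0.05 and, for power only, phi between 0.5 and −0.4. The direction of the error is not fixed.

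The consequence is confined to a supportive analysis. A reader might infer that the trial's success claim or its type I error depends on the switch. It does not: the responder test is outside the hierarchy in OLE SAP 7.8.4, and the formal rule in 7.8.2.2 is untouched. The remaining conflict is that 7.12.1.1 says clinical significance will be established by the mean difference, while 7.8.2.2 bases it on the primary test and the RCT SAP speaks only of further support. The SAP should be corrected.

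**What to change.** In OLE SAP 7.12.1.1:

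1. Delete the 36% switch, the 60% statement and the sentence making the required rate a function of the passive rate.
2. Whatever the passive rate, report the McNemar test with its sidedness stated, together with the paired difference in responder rates and its confidence interval, in participants with data from both periods.
3. Report the mean difference against the MCID separately, as 7.8.2.2.1 already plans.
4. Describe both results as supportive, consistent with 7.8.2.2.
5. If a statement on power is wanted, give it for 74 pairs over a stated range of discordance.

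The cost is SAP wording only: no new data, visits or participants, and no change to the primary analysis.

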7.13. Missing data

Item-level missing data will be handled as described in the SAP v6.0 for RCT Study (ID: SNS-PD-002).

1. INTRODUCTION

This document describes the statistical analysis plan (SAP) for SNS-PD-002, the multicenter randomized controlled trial portion described in the protocol Non-Invasive Brainstem Modulation for the Treatment of Non-Motor Symptoms in Parkinson's Disease: A Randomized Controlled Trial (RCT) and an Open Label Extension (OLE) Study (Brief title: STEM-PD). This analysis plan is meant to supplement the study protocol and specifically refers to procedures related to the RCT. Additional exploratory procedures of RCT data as well as procedures related to SNS-PD-003, the subsequent OLE portion of the study, will be specified in a separate SAP or Addendum. Any deviations from this analysis plan will be described in the clinical study report.

2. STUDY DESIGN

This is a randomized (1:1), multicenter, double-blind, controlled, pivotal clinical trial evaluating the safety and efficacy of twice daily time-varying caloric vestibular stimulation (tvCVS¹) treatments using a solid-state Device developed by Scion NeuroStim, Inc. (SNS), also known as ThermoNeuroModulation (TNMTM), for treating symptoms associated with Parkinson's disease (PD). The study will be conducted at 15 centers, at minimum, located in either the United States or the United Kingdom. The majority of centers will be in the United States. Up to 290 participants will screen for the randomized clinical trial (RCT) and will self-administer either tvCVS treatments or passive treatments twice daily in the home setting over a period of 12 weeks (84 days). Participants will continue to be enrolled into the RCT until at least 184 participants have randomized at which point competitive enrollment will be closed. The RCT will be immediately followed by an open label extension (OLE) study. The RCT and OLE have been separated into two distinct portions of the study with separate informed consent to enable the closeout and analysis of the RCT portion which will support regulatory submissions during the conduct of the OLE. However, anticipated participation in the OLE study will be a selection criterion for participating in the RCT, and thus, the two studies are defined within the context of a single protocol.

The proposed indication for use is for the treatment of symptoms of PD. For the RCT schedule of events, see Appendix 1.

2.1. STUDY OBJECTIVES

The null hypothesis for each of the primary and secondary outcomes states that the two treatment groups will show an equivalent change after 12 weeks of twice daily treatment with the TNMTM Device.

¹ tvCVS is the Scion NeuroStim - named method of applying caloric vestibular stimulation in a controlled, timevarying manner.

Primary Objectives: The primary objective of the RCT will be to test the hypothesis that TNMTM treatments provide safe and effective therapy for the reduction of non-motor symptom burden in participants with PD.

Secondary Objectives: This study will seek to establish whether TNMTM treatments provide adjuvant therapeutic effectiveness beyond that observed with dopamine replacement therapies (DRTs) to (1) provide global improvements, (2) improve activities of daily living related to motor function, (3) provide clinically meaningful change, (4) improve motor signs and symptoms and (5) improve quality of life (QoL) for participants with PD.

Safety Objectives: This study will seek to establish the safety of TNM^{TM} by monitoring adverse events and evaluating whether TNM^{TM} is associated with a worsening of balance, functional mobility and gait in PD.

Exploratory Objectives: This study will seek to establish the effectiveness of TNM^{TM} treatments for reducing specific non-motor symptoms (NMS) and in treating motor complications of dopamine replacement therapies. Outcomes will also evaluate the clinical meaningfulness of symptomatic improvements, explore the temporal kinetics of motor symptom response to treatment, evaluate the potential of TNM^{TM} treatments to improve gait, and provide additional measures to support clinical adoption and establish the health economics of TNM^{TM} as a therapy in PD.

2.2. STUDY ENDPOINTS

Primary Endpoint

• The change in The International Parkinson and Movement Disorder Society Nonmotor Rating Scale (MDS-NMS) (Chaudhuri 2020) total score.

Secondary endpoints will include changes to the following scores:

- The combined measure of The International Parkinson and Movement Disorder Society Unified Parkinson's Disease Rating Scale: Parts I, II and III(Makkos, Kovacs et al. 2018)
- The International Parkinson and Movement Disorder Society Unified Parkinson's Disease Rating Scale Part II: Motor Aspects of Experiences of Daily Living (MDS-UPDRS II) (Goetz, Tilley et al. 2008)
- The Overall Clinical Global Impressions Scale- Improvement (CGI-I) (Busner and Targum 2007)
- The International Parkinson and Movement Disorder Society Unified Parkinson's Disease Rating Scale Part III: Motor Examination (MDS-UPDRS III) (Goetz, Tilley et al. 2008)
- the Parkinson's Disease Questionnaire 39 summary index score (PDQ-39SI) (Jenkinson, Fitzpatrick et al. 1997)

Safety endpoints

• Adverse events (AEs) frequency

• The change in the Mini Balance Evaluation Systems Test (mini-BESTest) total score (Bloem, Marinus et al. 2016)

Exploratory endpoints

- The change in the following measures:
 - The Montreal Cognitive Assessment (MoCA)
 - The orally administered Symbol Digit Modality Test (oSDMT)
 - The Modified Schwab and England Activities of Daily Living Scale (S&E)
 - The Parkinson's Sleep Scale-2 (PDSS-2)
 - The Epworth Sleepiness Scale (ESS)
 - The Functional Assessment of Chronic Illness Therapy-Fatigue Scale (FACIT-F)
 - The Geriatric Depression Scale (GDS)
 - The Parkinson's Anxiety Scale (PAS)
 - The Patient Reported Outcomes in Parkinson's Disease (PRO-PD)
 - The MDS-NMS Non-Motor Fluctuations (NMF) Total Score
 - The Hoehn & Yahr score (H&Y)
 - Zarit Burden Interview (ZBI)
 - Unified Parkinson's Disease Rating Scale Part I: Mentation, Behavior and Mood (UPDRS I)
 - Unified Parkinson's Disease Rating Scale Part IV: Complications of Therapy
 - EncephaLogTM Finger Tapping Test (number of finger taps)
 - EncephaLogTM Timed Up and Go Test (TUG)
 - 3-meter TUG (time to complete)
 - 10-meter TUG (stride length, cadence, rotation time, time to complete)
 - The International Parkinson and Movement Disorder Society Unified Parkinson's Disease Rating Scale Part I: Non-Motor Aspects of Experiences of Daily Living (MDS-UPDRS I)
 - Domains of the MDS-NMS
 - Depression
 - Anxiety
 - Apathy
 - Psychosis
 - Impulse control and related disorders
 - Cognition
 - Orthostatic hypotension
 - Urinary
 - Sexual
 - Gastrointestinal
 - Sleep and wakefulness
 - Pain
 - Other

Treatment adherence and itemized answers from the following will be reported descriptively:

- a TNMTM Device usability survey
- Unified Parkinson's Disease Rating Scale Part IV (UPDRS IV)

4. SAMPLE SIZE DETERMINATION

The sample size for this study was set to achieve ~ 90% power to detect a minimal clinically important difference (MCID) of -2.64 points in the MDS-UPDRS: Part I (Horvath, Aschermann et al. 2017) for both the RCT and the first treatment period during the OLE. This estimated group sample sizes of 83 and 83 (166 total) to complete the RCT (assuming 10% attrition) achieves 89.2% power to detect a difference of 2.64 points in the MDS-UPDRS Part I total score for the null hypothesis that both group average change scores are equal and the alternative hypothesis that the average change score of the active treatment group represents greater symptomatic improvement than that of the passive treatment group given an estimated within group standard deviation of 5.32 points and a 2-sided significance level (alpha) of 0.05.

This sample size also achieves > 90% power to evaluate the primary endpoint of the STEM-PD OLE (see the STEM-PD OLE SAP for additional details).

Note that the primary outcome measure for the STEM-PD RCT is the MDS-NMS, not the MDS-UPDRS: Part I. However, the two scales are highly correlated (correlation coefficients = 0.75-0.85) (Chaudhuri, Schrag et al. 2019, van Wamelen, Martinez-Martin et al. 2021), and the MDS-UPDRS Part I has a pre-established MCID whereas the MDS-NMS does not. Given the high correlation reported for these two outcome measures in previous studies, an analysis was performed to estimate the MCID for the MDS-NMS. The MCID for the MDS-UPDRS: Part I is

2.64 points (Horvath, Aschermann et al. 2017). Since the estimated standard deviation of the MDS-UPDRS Part I for this study is 5.32 points, the MCID represents 49.6% of the standard deviation.

The standard deviation of the MDS-NMS scale has been reported as 65.87 points (Chaudhuri 2020). Using the same proportion of the standard deviation, the estimated MCID for the MDS-NMS scale for this study would be 32.7 points. Additionally, in an unpublished study analysis of participants from the original validation study, Martinez-Martin determined that among a cohort with MDS-UPDRS Part I scores greater than 10, which approximates the inclusion criterion for this study, the standard deviation of the MDS-NMS was 70.8 points. Utilizing a definition of 49.6% of the standard deviation, based upon the Martinez-Martin study, the MCID for the MDS-NMS scale would be 35.1 points.

Further, Norman et. al., 2003 (Norman, Sloan et al. 2003) suggested that the MCID be defined as 50% of the standard deviation. Using the standard deviation of 65.87, the MDS-NMS MCID would be 32.9 points. As noted above, however, the proposed study requires subjects to have an MDS-UPDRS Part I score of at least 9 at the study screen. Therefore, utilizing the standard deviation of 70.8 points (Martinez-Martin, *unpublished*), the MDS-NMS MCID would be 35.4 points². As such, the estimated MCID range for improvement in the MDS-NMS for this Statistical Analysis Plan is -32.7 to -35.4 points. While these values provide estimates for sample size calculations, the MCID for the MDS-NMS from data collected within this study using methodology described in section 7.6.1.3.

Notably, the sample size (184 to randomize), derived from the MDS-UPDRS Part I also achieves 85.7% power to detect the estimated MCID minimum of -32.7 and 92.8% power to detect the estimated MCID maximum of -35 points in the MDS-NMS.

Competitive enrollment will be used. Participants will continue to be enrolled until at least 184 are randomized in the RCT, and if there are additional participant withdrawals, they will not be replaced. Any participant who had entered the baseline period but had not yet randomized when the competitive enrollment target is achieved may be withdrawn from the study prior to randomization, and as a result, will not be included in any of the analyses. Data from all randomized study participants will be evaluated for analyses of safety and efficacy. The protocol has planned for up to 290 study participants to be screened. The sample size of 184 to randomize allows for attrition of 10% in the RCT as well as attrition of 10% in the first treatment period of the OLE while still maintaining adequate power to evaluate the primary endpoints of those studies.

[figure not shown]
